#### 13.1.3 STUDY 3 - Stakeholder perspectives on HS research (survey research)

SAMPLE. All participants in the cohort study. All recruiting clinicians.

DATA COLLECTION. Free-text response questions will be added to the cohort questionnaire instruments used at 12 months to consider satisfaction with treatments, barriers and facilitators to participating in research, and treatment choice (and factors in this).

An end of study questionnaire for recruiting clinicians will include free-text response questions about barriers and facilitators to engagement in future clinical studies of HS treatment.

DATA ANALYSIS. All data will be charted to the pre-defined thematic framework used in STUDY 2. Charted data will be synthesised with data from STUDY 2 and themes and sub-themes interpreted and summarised.

OUTPUT. Recommendations for the nature and form of future clinical studies in HS. Recommendations about processes and strategies that will support the success of future clinical studies in HS.

#### 13.1.4 Consensus workshop

Aim:

To achieve consensus amongst key stakeholders over priority research questions and proposed study designs for future research into HS

#### Objectives:

- 1. To identify up to three specific research questions suitable for future randomised controlled trials.
- 2. To agree key elements of the design including participants and setting, intervention, comparator and outcomes.

#### Methods:

SAMPLE. A maximum of 40 key stakeholders will take part with a balance between patient and clinician participants sought.

Participants will represent a range of clinical perspectives (including dermatologists, surgeons, general practitioners, nurses, commissioners), lay perspectives (including participants from the cohort study and carers/partners of people with HS), and research perspectives (including medical statisticians and clinical researchers).

PROCESS. A 1½ day consensus meeting will take place after completion of the cohort study and associated nested studies. Results from all studies (cohort, mixed methods, and outcome validation studies) will be presented. This information will be used to inform discussions over preferred study design and priority research questions. Standard consensus techniques will be used - similar to the methods used during James Lind Alliance Priority Setting Partnerships and core outcome set initiatives. This will involve adapted nominal group techniques, which incorporate whole and small group discussion to establish ranked priorities, and whole group voting as necessary. In this way we

will prioritise topics for future RCT comparisons. A private break-out room will be provided for patient-participants as necessary, so that they can manage their health needs (e.g. change dressings) and take some time-out of the conversations if needed.

There will be an opportunity to discuss decisions informally at the end of Day 1, which will allow time for wider debate and reflection, prior to the more detailed study design discussion to be held on Day 2.

DAY 1: An update on the findings of the THESEUS study will be presented, along with key background information about the previous James Lind Alliance Priority Setting Partnership results, and latest findings from the HISTORIC core outcome set group.

Facilitated, small group discussion will (i) seek to select treatments and comparators for inclusion in future research, and (ii) rank these according to importance. Whole group discussion will consider and synthesise small group rankings to produce a combined list of priority interventions and comparators to be evaluated in future RCTs -up to three priority research questions will be prioritised for further development during Day 2.

DAY 2: Working in 2-3 small groups with a mixture of stakeholders per group, we will formulate the key design elements of the prioritised study(s). This will include agreement over participants and setting; interventions (choice of interventions and comparators, type, dose and duration of medical interventions, type of surgery and degree of standardisation/training required for surgical interventions); and outcomes (primary and secondary outcomes, MID, duration and frequency of follow-up). The group will be asked to reflect on the practical challenges of delivering the proposed study, and will be encouraged to think of efficient study designs to answer the prioritised questions.

Whole group discussion (and where necessary voting) will synthesise proposals and finalise the research recommendations.

A final plenary will present the decisions of each small group to the whole group and will provide an opportunity to consider strategies to promote the refined research questions.

Throughout the workshop, experienced, independent facilitators from the UK Dermatology Clinical Studies Network will manage these processes and will ensure that all voices are heard in both the smaller and larger group interactions.

OUTPUT. An agreed list of up to three specific research questions for future research. Agreement over key design elements of the proposed future studies.

# 14 Safety reporting

The Medicines and Healthcare Products Regulatory Agency (MHRA) have approved a notification that a Clinical Trial Authorisation (CTA) is not required for this study, meaning THESEUS is a non-CTIMP study.

Safety reporting within this study will follow usual care pathways, as THESEUS is an observational study. Investigators will follow their usual processes of reporting adverse events, for example, yellow card reporting when required. There is no requirement to notify the research team in any expedited way of any adverse events.

The research team will collect data on any adverse events that occur during the treatment and followup stages of the study via routine data collection at the scheduled follow-up appointments.

#### 14.1 Contraception and pregnancy

Clinicians will follow usual practice when administering clindamycin or rifampicin, advising the participants of the need for a highly effective method of contraception.

Of note, the BNF recommends against the use of combined oral contraceptives if rifampicin is used for longer than 8 weeks. If pregnancy occurs, clinicians are to follow usual management strategies. If the participant wishes to switch to another treatment intervention, then they can do so. Or if they wish to withdraw from the study then the withdrawal processes as outlined in section 12 should be followed.

#### 15 Statistical considerations

#### 15.1 Sample size

With a sample size of 150, we will be able to estimate the proportion of participants who are hypothetically willing and eligible to be randomised in a clinical study to within a 95% confidence interval of  $\pm$  7%. We also wish to identify the case-mix of patients for each of the possible treatment options. From our patient survey, the least favourable treatment option (with 13%) was minor surgical operations, which would include deroofing of sinus tracts. 150 patients will provide us with 20 patients

opting for this non-medical intervention, which is sufficient to explore delivery in the IDEAL 2b evaluation.

## 15.2 Missing, unused & spurious data

Detail provided in the Statistical Analysis Plan (SAP), the data management plan and the qualitative analysis plan.

# 15.3 Procedures for reporting deviation(s) from the original SAP

These will be submitted as substantial amendments where applicable and recorded in subsequent versions of the protocol and SAP.

### 15.4 Termination of the study

While it is preferable for participants to remain within the intervention arm that they originally chose for the initial 6-month period, they may choose to discontinue or switch interventions at any time during the study. Reasons for switching treatment will be carefully documented.

There are no specific stopping rules for the entire study because participants are free to choose their intervention in consultation with their clinician.

#### 15.5 Inclusion in analysis

All enrolled participants will be included in the analysis. In the event of withdrawals, data up to the point of withdrawal of consent will be used.

# 16 Analysis

#### 16.1 Main analysis

We will describe the willingness of patients to be recruited overall and by patient intervention stated preferences and treatment uptake, including estimating intra-cluster correlation coefficients to explore clustering by centre. The group membership of each intervention will be described using descriptive statistics using data collected at baseline (month 0) (including demographics, clinical examination). Over the study period, we will report whether patients continue with and adhere to

their chosen intervention or whether they switch to alternative HS interventions during the study period. Treatment fidelity will be defined differently for each intervention option (e.g. oral clindamycin and rifampicin both 300mg twice daily for 10 weeks vs a one off surgical intervention) and will be described over the follow-up period. Within an intervention option, and where there is variation in fidelity, we will explore the possible predictors using regression modelling.

Where a patient switches intervention, we will report the reasons for this and again explore the possible predictors of switching (including intervention type, site, and other baseline demographics). Rates of loss to follow-up over the study period will be reported and we will examine whether there are any particular characteristics associated with response at 6 months.

Average change over time will be estimated for each efficacy outcome for each group with 95% confidence intervals. We will estimate the clustering/variability between surgeons/treating clinicians. Potential confounders of outcome will be assessed using regression methods.

Global assessment will be used as our anchor tool to allow estimation of MID. This will be used to dichotomise outcomes into those with clinically meaningful change and those without clinically meaningful change (stable or worse). Receiver operating characteristic curves will be generated, and the area under the curve (AUC) calculated as a measure of the outcome's ability to detect clinically relevant change. Youden's J index will be used to determine the minimal important change (MIC), and the MID will be calculated as the difference between the mean change in the improved and stable subgroups (17).

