#### Evidence explaining why this research is needed now

Despite being a relatively common condition, the evidence base for management of HS is relatively sparse, as highlighted in the Cochrane review first-authored by the lead applicant (2). Only 12 RCTs with a total of 615 participants were identified. European treatment guidelines are largely based on consensus as a result (3), yet surveys of dermatologists and surgeons conducted by team members have demonstrated idiosyncrasies in treatment strategies by different clinicians, suggesting that there may be undesirable variation in treatment in the UK. To prioritise the large HS research gaps, the lead applicant co-ordinated the HS James Lind Alliance Priority Setting Partnership (PSP), which published a top 10 list of future research priorities including both medical and surgical interventions (4). Our proposal incorporates several HS PSP priorities, including investigation of oral treatments, which was the number one priority, and surgical studies, covered by the sixth and eighth priorities.

Traditionally, there has been a lot of heterogeneity in outcomes across HS studies (5). The funding call from the HTA has come at an opportune time for HS research because core outcome domains have been established by the HIdradenitis SuppuraTiva cORe outcomes set International Collaboration (HISTORIC) (6, 7). The lead applicant is a member of the HISTORIC Steering Committee and so is well-placed to integrate this application with HISTORIC's ongoing work, which involves patients and clinicians in both Europe and North America. Our proposal meets all aspects of the Commissioning Brief by investigating second-line interventions for HS (both medical and surgical) in a prospective cohort study. The cohort study has been designed according to the IDEAL 2b framework for the evaluation of surgical interventions. Stage 2b, refers to the exploration stage in evaluating new surgical techniques and this will be with regard to the development of deroofing as an intervention for HS in the UK. We will work closely with HISTORIC to define outcome measurement instruments to assess treatment response and will provide estimates of Minimal Important Difference (MID) for each.

Recommendations for future primary research will be formulated in a consensus workshop attended by study participants, clinicians and researchers.

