#### 5.2 Secondary objectives

To determine:

- i) feasibility of recruitment for future RCTs of HS treatments;
- ii) choice and characterisation of study interventions (dose of medication, type of surgical techniques used);
- iii) current patient pathways and understanding of what influences patients' and clinicians' treatment choices;
- iv) choice, feasibility and responsiveness of outcome measure instruments, including evaluation of minimum important difference (MID) to inform sample size calculations; and
- v) consensus-agreed recommendations for future study designs.

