#### 11.1 Assessments / Data collection

The schedule of assessments is summarized in figure 1. A window of 2 weeks is permissible either side of the intended follow up date. Safety blood tests (full blood count, renal function, liver function) will be required at baseline and after 4 weeks only for participants choosing the clindamycin and rifampicin intervention. These blood tests are part of usual care and will be carried out within the hospital setting. The participants treating clinician within secondary care will review the blood results and inform the participant whether they can start/continue with their chosen clindamycin and rifampicin intervention.

Efficacy outcome measures will include the six core domains recommended by the HISTORIC core outcome set initiative for HS: (i) Pain (using a numeric rating scale) (ii) HS-specific quality of life (HiSQOL), (iii) global assessment, (iv) progression of course (flare frequency), (v) physical signs and (vi) symptoms (drainage resulting in need for dressings and fatigue) (7). HISTORIC-recommended instruments will be employed where these are available, plus a generic measure of quality of life (EQ-5D). We will report completeness of each outcome at each time point.

Pain NRS will be measured at the baseline appointment and then on a daily basis for the first 12 weeks following treatment commencement via mobile telephone text message.

Figure 1. Schedule of interventions and assessments

Review number	-1	0	1	2	3	4
Planned month	-1	Baseline	3	6	9	12
Screening logs	Х	Х				
Eligibility assessment	Х	Х				
Demographics and consent		Х				
Clinical examination including Hurley stage		Х	Х	Х	Х	Х
Interventions for which participant is potentially eligible		Х				
Intervention received, with reasons for choice (including treatments switched after baseline)		X	Х	Х	Х	Х
Outcomes						
HS quality of life questionnaire (HiSQOL)		Х	Х	Х	Х	Х

Dermatology Life Quality Index (DLQI)	Х	Х	Х	Χ	X	
EQ5D-5L questionnaire	Х	Х	Х	Х	Х	
Pain visual analogue scale (VAS/NRS)	Х	Х	Х	Х	Х	
Pain score (via text message)	12 we	12 weeks from start of intervention				
Need for dressings	Х	Х	Х	Х	Х	
Fatigue questionnaire	Х	Х	Х	Х	Х	
Patient global assessment	Х	Х	Х	Х	Х	
Anchor question for change in severity		Х	Х	Х	Х	
Flares	Х	Х	Х	Х	Х	
Assessment of HS physical signs	Х	Х	Х	Х	Х	
Adverse effects of study treatment		Х	Х	Х	Х	
Treatment fidelity		Х	Х	Х	Х	
End of study questionnaire (participants and clinicians)					Х	

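### The MID contrast does not limit the improved group to the smallest improvement and leaves its reference group unclear, so trials sized on it risk being underpowered for the minimal difference

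*Protocol*

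**What the plan says.** Protocol section 16.1 takes these steps in order.

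- Anchor: "Global assessment will be used as our anchor tool to allow estimation of MID". The section does not list the anchor's categories or the cut-off for improvement.
- Dichotomy: the anchor splits participants into "those with clinically meaningful change and those without clinically meaningful change (stable or worse". ROC curves and the AUC follow from this split.
- MIC: a threshold chosen by Youden's J.
- MID: "the MID will be calculated as the difference between the mean change in the improved and stable subgroups".

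The MID is meant to be a minimal quantity with a practical use. The Background, under the heading on why the research is needed now, says the team "will provide estimates of Minimal Important Difference (MID) for each" outcome instrument. Section 5.2 describes the objective as "including evaluation of minimum important difference (MID) to inform sample size calculations". Section 13.1.4 lists the MID among the outcome matters that the consensus workshop will settle when it designs future trials.

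**The concern.** A minimal important difference should describe people who improved by the smallest amount that matters. The MID sentence does not restrict *improved* in that way. The only grouping that section 16.1 sets up is a two-way split, and its upper group has no ceiling. Read naturally, it holds small and large responders together. Its mean change is then that of a typical responder, and subtracting the stable mean gives a typical-responder difference under the name of a minimal one.

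The reference group is also unsettled. The dichotomy pools stable with worse, while the MID sentence names only *stable*. No separate stable group is defined, and the two readings give different answers.

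Required sample size varies as 1/MID². If the contrast is larger than the minimal one, a later trial that takes it as the target difference is too small to detect the minimal difference with the power intended.

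**Working it through.** The protocol gives no MID value, SD, anchor distribution or future trial size, so there is no figure to reproduce. The check compares three contrasts under assumed inputs. Let *p* be the share and *m* the mean change in each anchor category.

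- (a) smallest improvement minus stable: m_min − m_stable
- (b) all improved minus stable: (p_min·m_min + p_much·m_much)/(p_min + p_much) − m_stable
- (c) all improved minus stable or worse: the first term of (b) minus (p_worse·m_worse + p_stable·m_stable)/(p_worse + p_stable)

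**Direction.** By algebra:

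- (b) − (a) = [p_much/(p_min + p_much)]·(m_much − m_min). This is positive whenever larger improvers exist and change more on average.
- (c) − (b) = [p_worse/(p_worse + p_stable)]·(m_stable − m_worse). This is positive whenever worsened participants are pooled in and change less favourably than the stable.

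**A middle case (all inputs assumed).** Shares are 10% worse, 30% stable, 40% minimally improved and 20% much improved. Means are −0.5, 0, 0.5 and 1.0 SD.

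- (a) = 0.50
- (b) = (0.40×0.5 + 0.20×1.0)/0.60 = 0.40/0.60 = 0.67
- (c) = 0.667 − (0.10×(−0.5) + 0.30×0)/0.40 = 0.667 + 0.125 = 0.79

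**Effect on a later two-arm trial** (SD 1, two-sided 0.05, 90% power, normal approximation). The size per arm is n = 2(1.960 + 1.282)²/d², about 21.0/d². Power at a true difference of 0.5 SD is Φ(0.5·√(n/2) − 1.96).

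| Contrast used as target | d (SD) | n per arm | Power at 0.5 SD |
|---|---|---|---|
| (a) | 0.50 | 85 | 90% |
| (b) | 0.67 | 48 | 69% |
| (c) | 0.79 | 34 | 54% |

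**Range.** Four mixes of worse/stable/minimal/much improved were used: 10/30/40/20, 20/30/25/25, 25/25/15/35 and 5/45/45/5 per cent. Each was crossed with three sets of means in SD: (−0.5, 0, 0.5, 1.0), (−0.3, 0, 0.5, 0.8) and (−0.5, 0, 0.5, 1.5).

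- (b)/(a) ran from 1.06 to 2.4, giving 75 down to 15 per arm and power at 0.5 SD of 87% down to 28%.
- (c)/(a) ran from 1.12 to 2.9, giving 68 down to 10 per arm and power of 83% down to 20%.
- With a 0/50/50/0 mix all three contrasts are equal.

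**Imperfect anchor.** A latent-normal simulation had mean change 0.3 SD and anchor cut-points at −0.5, 0.5 and 1.25.

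| Anchor–change correlation | (a) | (b) | (c) | (b)/(a) |
|---|---|---|---|---|
| 1.0 | 0.82 | 1.20 | 1.60 | 1.46 |
| 0.7 | 0.57 | 0.84 | 1.12 | 1.47 |
| 0.3 | 0.25 | 0.36 | 0.48 | 1.44 |

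The ordering and the ratio persist, but a weak anchor shrinks all three. At correlation 0.3 even (c) lies below the 0.82 that (a) gives with a perfect anchor.

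**The case against.** The strongest reply has four parts.

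1. *The pooled group belongs to the ROC step.* A reader might infer that the MID subtracts the mean of everyone stable or worse. The text does not say so: the pooling is stated for the dichotomy, and the MID sentence says *stable*. What stands is that adjacent sentences use different terms and no separate stable group is defined, so contrast (c) is only a possible reading.
2. *Nothing says that all improvers are included.* True: that is an inference from a two-way split without a ceiling. The SAP was not available to this review and may list the categories. A stricter cut-off there would not help, because it would remove the smallest improvers and raise the improved mean. Only an upper limit would help, and section 16.1 sets none.
3. *The resulting MID may not be too large.* A reader might infer that it must be, and that later trials must be too small. The documents do not support that. The size depends on an unknown anchor distribution, and a weak anchor pulls every contrast down. The relative excess over the minimal contrast does stand. Attenuation is a separate bias, and nothing suggests that the two cancel.
4. *Later trialists have other inputs.* They will also have the MIC, and the workshop will discuss the MID, so underpowering is a risk and not a certainty. But the MIC is a separately named quantity, and section 5.2 ties sample size to the MID.

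Improved minus stable is also a deliberate choice, made in a sentence with a methods reference that could not be consulted here.

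**Conclusion.** The point holds as a relative and conditional one. Section 16.1 fixes the MID as improved minus stable without restricting improvement to the smallest category, so it estimates a typical-responder difference and not the minimal one promised in the Background and section 5.2. It exceeds the minimal contrast whenever larger improvers are present and change more on average. It does so further if worsened participants are counted in the reference, which the wording leaves open.

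The numbers illustrate this and are not estimates for this cohort. They rest on assumed category shares and means, SD 1, and the premise that the smallest improvement category marks the minimal important change. The excess can be nil, slight or large across the mixes tried. The primary outcome is unaffected. This is a cheap improvement to a secondary objective.

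**What to change.** In section 16.1, and in the SAP where it repeats the definition:

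- Define the MID as mean change in participants in the smallest-improvement anchor category minus mean change in those in the unchanged category, with a 95% CI.
- Keep participants who worsened, or who improved by more than the smallest category, out of that contrast.
- Use the split of improved versus stable or worse only for the ROC curve, the AUC and the Youden-based MIC.
- Report mean change for every anchor category, so that readers can see the gradient and form other contrasts.
- State the anchor's categories and which item is the anchor. Figure 1 in section 11.1 lists a patient global assessment, collected from baseline, and separately an "Anchor question for change in severity", collected at follow-up only.

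This is a wording change and needs no new data. The cost is precision. The 95% half-width is 1.96·√(1/n₁ + 1/n₂) in SD units, taking 150 participants before attrition and within-category SD 1.

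- Middle case: √(1/60 + 1/45) gives 0.39 SD, against √(1/90 + 1/45), which gives 0.36 SD, for all improved.
- A mix with 30% unchanged, 25% slightly improved and 50% improved in all: 37.5 versus 45 participants gives 0.43 SD, against 75 versus 45, which gives 0.37 SD.

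The loss is modest, but both intervals are wide if the MID is near 0.5 SD, which is a further reason to report the interval.
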